5.8 CONCOMITANT THERAPY

All medications received by the subject at any time prior to the Screening Visit and taken within 3 months before the Screening Visit, during the interval between the Screening Period and Randomization and those taken throughout the trial will be recorded on the appropriate electronic case report form (eCRF). The site may rely on subject report for this information. All subjects must be questioned about concomitant medication at each visit. All concomitant medication, both prescribed and over-the-counter, must be recorded in the eCRF. This includes drugs used on a chronic and as needed basis.

Medications that are indicated as prohibited in the Exclusion Criteria must not be used after the screening visit during the interval between the screening period and randomization or during the trial.

The following treatment/drugs will be allowed during the study.

- i. Statins are permitted as concomitant medications; however, patients will be monitored for statin related toxicity when it is co-administered.
- ii. Glycemic control medications will be permitted as concomitant medications, including antidiabetic drugs such as metformin, sulfonylureas, dipeptidyl peptidase 4 (DPP-4) inhibitors and insulin.
- iii. Treatment for common illness during the study may be allowed.
- iv. For any required concomitant medication, the patient must be on a stable dose for 3 months at study entry and patients must continue with their current drug regimen without any change in dosage.

5.9 RESCUE MEDICATION AND ADDITIONAL TREATMENT(S)

The Investigator at his/her discretion will be allowed to offer a rescue medication for clinically significant conditions correlated with the laboratory findings, if required, however, such interventions shall be recorded in the eCRF with description of type of intervention, dose and duration. If medication given is in violation to the protocol, then such subjects will be withdrawn from the trial.

Approved by:
[name]

Protocol No. SARO.16.004
Version No.: 6.0

Subjects on antidiabetic drug shall also be assessed on scheduled visits for hyperglycemia/hypoglycemia and rescue medication will also be allowed if required. Treatment for such conditions should be initiated as soon as the need for treatment is identified, in accordance with treatment guidelines and standard of care, and should be adjusted as necessary to treat the subject's condition(s). All treatment with these drugs should be recorded on the appropriate case report form (CRF).

Investigator's shall advise subjects to report at the site for any inconvenience during the course of trial

5.10 RESTRICTIONS

Patients are not permitted to take thiazolidinedione (pioglitazone, rosiglitazone), chemotherapy, or other investigational medications during the study duration.

Patients also should not take any over-the-counter medications or complementary and/or alternative medications without prior consultation of the Investigator.

The PI should be alerted if, during the course of the study, a patient requires a new medicine or therapy or a changes to an established dosing regimen.

5.11 OVER DOSE AND DRUG INTERACTION

A series of 15 horizontal black bars of varying lengths, decreasing in length from left to right. The bars are evenly spaced and extend across the width of the frame.

5.12 TREATMENT COMPLIANCE

The subjects will be asked to bring the container of the study medication on the next follow-up visit; compliance for dosing will be assessed by examination of the container and tablet count by study personnel and documentation on individual drug accountability logs.

6 OBSERVATIONS

6.1 EFFICACY

6.1.1 Primary Endpoint

1. Improvement in ALP levels after 16 weeks of Saroglitazar magnesium 2 mg and 4 mg treatment.

6.1.2 Secondary Endpoints

1. To compare the effect of Saroglitazar magnesium (2 mg and 4 mg) and placebo on below mentioned parameters following a 16-week treatment:
 - i. Change from baseline in ALP at Week 4, Week 8, Week 12 and Week 16 in Saroglitazar magnesium as compared to placebo.
 - ii. Change from baseline in lipid profile (TG, TC, HDL, LDL, and VLDL) at Week 4, Week 8, Week 12 and Week 16 in Saroglitazar magnesium as compared to placebo.
 - iii. Change from baseline in liver biochemistries (GGT, ALT, AST, Bilirubin and albumin) at Week 4, Week 8, Week 12 and Week 16 in Saroglitazar magnesium as compared to placebo.
 - iv. Change from baseline in serum total bile acids, at Week 4, Week 8, Week 12 and Week 16 in saroglitazar as compared to Placebo.
 - v. Change from baseline in 7 α -hydroxy-4-cholesten-3-one (C4) at Week 16 in saroglitazar as compared to Placebo.
 - vi. Change from baseline in fibroblast growth factor 19 (FGF 19) at Week 16 in saroglitazar as compared to Placebo.
2. Proportion of patients with ALP improvement, i.e. 15%, 20%, 30%, 40% and normalization at Week 8 and Week 16.
3. Change in QoL at Week 16 by using PBC40.
4. Change from baseline in ALP in patients who are unable to tolerate UDCA at week 16 in Saroglitazar 2 mg and 4 mg as compared to Placebo.
5. Safety and tolerability of Saroglitazar magnesium 2 mg and 4 mg.
6. Pharmacokinetics of Saroglitazar.

**Zydus Discovery
DMCC**

CLINICAL TRIAL PROTOCOL

Saroglitazar Magnesium – Phase II

SARO.16.004

CONFIDENTIAL

PAGE 47 OF 82

Pharmacokinetics of Saroglitazar Magnesium will be performed in patients with PBC. The samples will be collected at Pre-dose (0.0), 0.5, 1.0, 2.0, 3.0, 4.0, 6.0, 8.0, 10.0 and 24 hours post-dose on Visit 3 and Visit 7. In addition, pre-dose sample will be collected at Visits 4, 5, and 6.

The following pharmacokinetic parameters will be evaluated:

- i. Peak Plasma concentration (Cmax)
- ii. Time to reach peak Plasma concentration (Tmax)
- iii. Area under Plasma concentration vs. time curve till the last time point (AUC0-t)
- iv. Area under Plasma concentration vs. time curve extrapolated to the infinity (AUC0- ∞) after first dose
- v. Area under plasma concentration vs. time curve in a 24 h dosing interval (AU τ)
- vi. Elimination rate constant (λ_z)
- vii. Elimination half-life (t_{1/2})
- viii. Apparent Volume of distribution (Vd/F)
- ix. Apparent Clearance (CL/F)
- x. Minimal or Trough plasma concentration (C_{min}) -for last dose only
- xi. Accumulation index calculated as a ratio of AU τ (last dose)/AU τ (first dose)
- xii. Fluctuation index.

6.2 SAFETY

To assess the safety of Saroglitazar magnesium in the study population over the duration of study.

- Adverse event(s): frequency and severity of AE / SAEs, drop-out due to AEs/SAEs for all subjects enrolled will be recorded. All AEs, will be assessed using Council for International Organizations of Medical Sciences (CIOMS) criteria using:
 - Causality
 - Severity
 - Seriousness
 - Expectedness
- Clinical laboratory testing (hematology, clinical chemistry and urinalysis)

Approved by:
[name]

Protocol No. SARO.16.004
Version No.: 6.0

- Twelve-lead electrocardiogram (ECG)
- Vital signs
- Body weight and height (at screening)
- The physical examination will consist of an evaluation of the head, neck, eyes, ears, nose, throat, chest, heart, lungs, abdomen, skin, extremities, and the neurological and musculoskeletal systems.

All AEs will be captured and notification sent to the Sponsor. All AEs will be captured in eCRF. At a minimum, SAEs will be reported in the CRFs as per the timelines defined in the Protocol in adverse event section. However, each research institution's IRB/IEC reporting requirements may contain shorter timelines.

Serious adverse events reporting must comply with the United States of Food and Drug Administration (USFDA) reporting requirements and IRB/IEC reporting requirements.

Every effort should be made to ensure that the protocol required tests and procedures are completed as described. However, it is anticipated that from time to time there may be circumstances, outside of the control of the Investigator that may make it unfeasible to perform the test. In these cases, the Investigator will take all steps necessary to ensure the safety and well-being of the subject. When a protocol required test cannot be performed the Investigator will document the reason for this and any corrective and preventive actions which he/she has taken to ensure that normal processes are adhered to as soon as possible.

The trial team will be informed of these incidents in a timely fashion.

All biological samples will be assayed by a Sponsor-identified CAP and/or CLIA-certified laboratory, using analytical methods in compliance with standard and validated methodologies, with adherence to written standard operating procedures (SOPs).

Details regarding the sample processing, handling, storage, and shipment will be offered separately in the study-specific central laboratory manual prior to the initiation of the trial.

6.2.1 Appropriateness of Measurement

The endpoints chosen for the given study [safety and efficacy] are appropriate for the assessment of outcome of the study.

6.2.2 Abnormal Laboratory Findings

In addition, a clinically significant value outside the normal or reference range in a routine safety assessment, such as clinical laboratory, vital signs or ECG, may signify an adverse finding. Additional examinations or repetition of test will be performed as medically indicated.

If the Investigator considers the abnormality as of major relevance, he/she should also record this as an AE. If the findings contribute to a clinical diagnosis (e.g. hepatitis in case of increased liver enzymes), then this diagnosis should be recorded as AE.

The criteria for determining whether an abnormal objective test finding should be reported as an AE are as follows:

1. Test result is associated with accompanying symptoms, and/or
2. Test result requires additional diagnostic testing or medical/surgical intervention, and/or
3. Test result leads to change in study dosing or discontinuation from the study, significant additional concomitant drug treatment or other therapy, and/or
4. Test result leads to any of the outcomes included in the definition of SAE, and/or
5. Test result is considered to be an AE by the Investigator.

For any abnormal test result that meets one of the above conditions except for the last condition, the Investigator will provide a justification for not reporting the abnormal test finding as an AE.

Each AE shall be evaluated for the severity, duration, resolution, action taken and its association with the study treatment. The study participant may be withdrawn or terminated from the study depending on the seriousness of the adverse effects.

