9.4 PROCEDURES

9.4.1 Adverse Events

All AEs occurring during the course of the clinical trial (i.e., from signing the informed consent onwards) will be collected, documented and reported to the Sponsor by the Investigator according to the specific definitions and instructions detailed in this section.

An AE is defined as any untoward medical occurrence in a clinical investigation subject administered a pharmaceutical product and which does not necessarily have to have a causal relationship with this treatment.

Any medical condition already present at screening should not be reported as an adverse event unless the medical condition or signs or symptoms present at baseline changes in severity or seriousness at any time during the study. In this case, it should be reported as an adverse event.

Clinically significant abnormal laboratory or other examination (e.g. electrocardiogram) findings that are detected during the study or are present at screening and significantly worsen during the study should be reported as AEs. The investigator will exercise his or her medical and scientific judgment in deciding whether an abnormal laboratory finding or other abnormal assessment is clinically significant. Clinically significant abnormal laboratory values occurring during the clinical study will be followed until repeat tests return to normal, stabilize, or are no longer clinically significant. Any abnormal test that is determined to be an error does not require reporting as an AE.

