9.4.2 Serious Adverse Event

A serious adverse event is any adverse event occurring at any dose or during any use of Sponsor's product that:

- Results in death;
- Is life threatening;
- Results in persistent or significant disability/incapacity;
- Results in inpatient hospitalization or prolongs an existing inpatient hospitalization;
- Is a congenital anomaly/birth defect;
- Is another important medical event that may not result in death, be life-threatening, or require hospitalization may be considered serious when, based upon appropriate medical judgment, they may jeopardize the patient or subject and may require medical or surgical intervention to prevent one of the outcomes listed above.

Serious Adverse Event Reporting-Procedures for Investigators:

Initial Reports:

Any serious adverse event, or follow-up to a serious adverse event, including death due to any cause that occurs to any subject from the time the consent is signed through 7 days following cessation of treatment, whether or not related to the Sponsor's product, must be reported to the Sponsor within 24 hours of the knowledge of the occurrence to investigational site.

Additionally, any serious adverse event, considered by an Investigator who is a qualified physician to be related to the Sponsor's product that is brought to the attention of the Investigator at any time outside of the time period specified in the previous paragraph also must be reported immediately to the Sponsor.

To report the SAE, complete the SAE form electronically in the electronic data capture (EDC) system for the study. When the form is completed, CRO/Sponsor Safety personnel

**Zydus Discovery
DMCC**

CLINICAL TRIAL PROTOCOL

Saroglitazar Magnesium – Phase II

SARO.16.004

CONFIDENTIAL

PAGE 69 OF 82

will be notified electronically and will retrieve the form. If the event meets serious criteria and it is not possible to access the EDC system, send an email to CRO/Sponsor or call the CRO/Sponsor SAE hotline (phone number listed below), and email the completed paper SAE form to CRO/Sponsor (email listed below) within 24 hours of awareness. When the EDC system becomes available, the SAE information must be entered within 24 hours of the system becoming available.

Safety Contact Information:

[name] [name]

[REDACTED]

Follow-Up Reports

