8.3.2 Adverse Events

The applicable definition of an Adverse Event (AE) is in the study protocol. All AEs occurring from when a patient signs informed consent to when a patient exits the study will be accounted for in the reporting. Analysis and presentation of AEs occurring during the screening period will be separated from those occurring during the investigational period where a comparative evaluation of treatment-emergent AEs is intended. A treatment-emergent AE is an event not present prior to exposure to investigational product or any pre-existing event that worsens following exposure to investigational product. The period for treatment-emergent AE analysis starts from the first exposure to the investigational product until the patient exits the study.

Descriptive summaries (frequencies and percentages) for specific AEs will be presented by system organ class and preferred term according to the Medical Dictionary for Regulatory Activities (MedDRA Version 19.1) dictionary by treatment group and overall. In addition to an overall presentation of all AEs, reports will be generated for special classes of AEs such as investigational product related AEs, serious AEs, Maximum severity and AEs resulting in treatment discontinuation by treatment group. These reports will be supported by individual patient listings, as necessary.

Document Title:	Statistical Analysis Plan		
Version Number:	2.0	Date:	11 Nov 2019
Protocol Number:	SARO.16.004	Sponsor Name:	Zydus Discovery DMCC

Adverse events will be counted by the number of events as well as the number of subjects. For the summaries which count the number of patients by treatment group and overall, multiple AEs with the same MedDRA preferred term within the same patient will only be counted once.

Descriptive summaries (frequencies and percentages) for number of subjects experiencing AEs will also be presented.

Only patient listings will be provided for AEs that occur after signing informed consent but prior to exposure to investigational product. These listings will comprise all events occurring during this period in any patient who consented to participate in the study.

These listings will at least contain but not limited to information such as onset and resolution times, maximum severity, causal relationship to study treatment and action taken.

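### Protocol 6.2.2 allows a test finding that changed or stopped dosing to go unrecorded as an AE, while the SAP counts treatment stops only through AE records

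*Protocol*

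**What the plan says.** **Protocol 6.2.2** sets out five conditions, any one of which is enough for an abnormal objective test finding to be reported as an AE. Condition 3 reads "Test result leads to change in study dosing or discontinuation from the study" and condition 4 reads "Test result leads to any of the outcomes included in the definition of SAE". Condition 5 is that the investigator considers the result an AE. The closing sentence begins "For any abnormal test result that meets one of the above conditions except for the last condition" and continues "the Investigator will provide a justification for not reporting the abnormal test finding as an AE". It does not limit the acceptable reasons, require review, or say where the justification is kept. The same section says that where a finding contributes to a clinical diagnosis, "then this diagnosis should be recorded as AE".

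**Protocol 9.4.1** says of clinically significant abnormal results: "findings that are detected during the study or are present at screening and significantly worsen during the study should be reported as AEs". The investigator judges significance. The only exemption stated for an abnormal test is one found to be an error.

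**Protocol 4.4.1** stops or interrupts study drug on ALT/AST, eGFR, bilirubin, CK, amylase and lipase, haemoglobin or haematocrit, platelet and white-cell criteria.

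**SAP 8.3.2** plans special AE reports that include "serious AEs, Maximum severity and AEs resulting in treatment discontinuation by treatment group". The disposition table in SAP section 5 counts patients who left the study, with the reason.

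**The concern.** Two sections give different instructions for the same event. A site following 9.4.1 records a clinically significant laboratory abnormality as an AE. A site following 6.2.2 may leave it off with a written reason, even if it led to study drug being held or stopped. Recording can then differ between investigators across some 10 to 12 sites.

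This matters because the AE record is the only planned route by which a drug stop reaches a table of stops. Many of the events that oblige a site to stop the drug are laboratory values, which is the class of finding the opt-out covers. The rate of AEs leading to discontinuation is a main tolerability measure. Safety and tolerability are among the trial's stated purposes, and the interim results inform the dose for phase III.

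**Working it through.** The plan states no figure on this point, so the check is a comparison of text, followed by simple arithmetic for scale.

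**Step 1. Scope of the opt-out (Protocol 6.2.2).** There are five conditions and only the last is excepted, so conditions 1 to 4 can be justified away. Condition 3 speaks of a dosing change or discontinuation from the study. By ordinary reading, stopping or interrupting study drug is a change in dosing.

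**Step 2. Laboratory triggers in Protocol 4.4.1.**

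| Group | Laboratory triggers |
|---|---|
| ALT/AST list, items a–d | 4 |
| eGFR | 1 |
| Immediate-stop list, items a–f | 6 |
| Total | 4 + 1 + 6 = 11 |

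Five of these rest on liver tests (ALT/AST a–d and bilirubin). The other six do not (eGFR, CK, amylase and lipase, haemoglobin or haematocrit, platelets, white cells): 11 − 5 = 6.

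**Step 3. Where an unrecorded stop could still appear.**

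| Planned output | Would it show the stop? |
|---|---|
| AE-discontinuation report (SAP 8.3.2) | No; it needs an AE record |
| Action-taken item in Table 4 (Protocol 9.4.3) | No; it is an attribute of an AE |
| Disposition (SAP 5) | Only if the patient also leaves the study |
| Extent of exposure (SAP 8.3.1) | Only as a shorter treatment duration, with no reason; an interruption does not change the first and last dose dates |
| Laboratory tables, shift table and listings (Protocol 8.3.3, SAP 8.3.5) | The value appears, but no planned link to the stop |
| Interim analysis (SAP 2.5) | Named content is liver biochemistries and lipids as efficacy, demographics and AEs, with no subject-level listing; a stop on one of the six non-liver triggers would appear in none of these |

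**Step 4. Scale.** Change in an arm's rate per omitted stop = 1 / arm size. With 12 per arm (SAP 4), 1/12 = 8.3 percentage points. The interim number depends on what the 24 active randomized subjects means. If they are spread evenly over three arms, 24/3 = 8 and 1/8 = 12.5 points. If they are on saroglitazar only, 24/2 = 12 and the figure is again 8.3 points. No rate of laboratory stops, or of use of the opt-out, is given, so no expected loss can be computed.

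**The case against.** The strongest reply is that 6.2.2 makes reporting the default and asks for a reason to depart from it, which can be read as a safeguard. There are legitimate reasons: the diagnosis may already be the AE (6.2.2), or the result may be an error (9.4.1). Section 9.4.1 still tells the site to report clinically significant findings. Protocol 6.2 requires drop-outs due to AEs to be recorded, and the immediate-stop text in 4.4.1 speaks of following an adverse event to resolution. On this view, what is left is a rule-driven stop that the investigator judges not clinically significant and explains in writing.

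Much of this stands, and it marks where the gap is clearest. It does not close the gap: a justification held outside the AE record does not reach an AE table, and the reasons are not limited to those two.

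A reader might infer three stronger claims that the documents do not support.

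- **SAEs could be lost.** The opt-out concerns the test finding. An SAE, related or not, "must be reported to the Sponsor within 24 hours of the knowledge of the occurrence to investigational site", with no such opt-out. Condition 4 is a wording conflict, not a shown loss of SAEs.
- **The stops vanish altogether.** They can be absent from AE tables, but abnormal values remain in the final laboratory tables and listings.
- **Safety oversight is blinded to them.** Protocol 7.6 names liver elevations as a review item alongside AEs. The limb of 4.4.1(g) that counts patients meeting a to f works from laboratory criteria, and 9.4.4 sets its own laboratory threshold for 24-hour reporting.

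The separate major-relevance wording in 6.2.2 is a minor matter. The section opens with clinical significance, and its five conditions are broader.

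**Conclusion.** The point holds as a recording and reporting gap. Sections 6.2.2 and 9.4.1 conflict for findings that changed or stopped dosing. Because the SAP has no summary of drug stops independent of AE records, a justified-away stop would be missing from the AE-discontinuation table and from the interim adverse-event summary. Each omission lowers an arm's rate by 8.3 percentage points at 12 per arm. That is a measure of scale, not a forecast.

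This rests on two assumptions: that a drug stop counts as a dosing change under condition 3, and that a patient taken off drug is not automatically withdrawn from the study. The documents do not state the second either way. If stopping drug always meant leaving the study, disposition would show a permanent stop, though still not an interruption.

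The primary ALP endpoint definition is untouched. The weakness is in the tolerability comparison. It should be corrected because the remedy is small and the trial informs the choice of dose.

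**What to change.** Four changes, all about recording; no dose or stopping rule is altered.

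1. In Protocol 6.2.2, remove conditions 3 and 4 from the justification route. A result meeting either is recorded as an AE unless it is found to be an error (as 9.4.1 allows) or is already captured by a recorded diagnosis (as 6.2.2 requires). Without these two exceptions the new text would contradict 9.4.1 and double-count some events.
2. Cross-refer condition 4 to 9.4.2.
3. Use the clinical-significance wording of 9.4.1 in 6.2.2 in place of the major-relevance wording.
4. Add to the SAP a summary, by arm, of study-drug discontinuation and interruption by reason that does not depend on an AE record, and include it in the interim outputs.

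The cost is a few sentences of protocol text, a memo to sites, a few more AE forms and one more table. Item 4 also needs the reason for each stop to be captured in the eCRF independently of the AE form, if it is not already.
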